11.3.1. Date derivation

Partial dates will not be considered as missing or not evaluable date. In case day is missing, 15th of month is used. In case day and month are missing, 30th of June is used.

Partial or missing initial and end dates for exacerbation will not be considered to measure the length of an exacerbation.

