3.1.1.1. Date of onset and end date of AECOPD

The date of onset is the first day (of at least 2 consecutive days) of worsening symptoms of COPD, as determined by the Investigator according to the Anthonisen criteria.

The end date should be based on when the investigator determines that the AECOPD symptoms have resolved. In determining this end date, consideration should be given to symptoms recorded in the electronic Diary Card and subject assessment during the phone calls.

Both start and end date of each confirmed AECOPD occurring from the screening visit to study conclusion will be recorded in the eCRF.

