6.3.5. Severity and duration of AECOPD

Total number of exacerbations recorded during the study, exacerbation rate (number of exacerbation per patient-year) and the proportion of COPD patients experiencing a certain number of exacerbations will be presented overall and per bacterial/viral species. The exacerbation rate per year will be reported with and without correction for early withdrawal (see Section 11.3).

Total number of exacerbations recorded during the study, the mean exacerbation rate per year and the proportion of COPD patients experiencing a certain number of exacerbations will be presented overall and divided by AECOPD severity.

The number and proportion of COPD patients experiencing a certain number of exacerbations will be presented overall and by GOLD grade at enrolment.

CONFIDENTIAL

201112 (EPI-NTHI-001 BOD APA)
 Statistical Analysis Plan Amendment 2 Final

The number of patients that report at least 1 AECOPD will be tabulated and descriptive statistics (N, mean, median, SD, minimum, maximum, first and third quartiles) on the average length of AECOPD episodes, as estimated by the investigator, will be presented, for any, mild, moderate and severe AECOPD.

Number of days between 2 consecutive exacerbations, as estimated by the investigator, will be summarized using the same descriptive statistics.

Descriptive statistics of the number of patients according to their percentage of days within an exacerbation period out of the total observation period as estimated by the investigator will be presented. For this analysis, the exacerbations for which the end date was unknown were not excluded and the length was estimated by the investigator as the average length per severity grade.

Results from the chest X-rays during exacerbation visit will be tabulated.

The percentage of scheduled visit in which the status of the patient is stable/recovered, or not recovered will be tabulated.

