11.3. Handling missing data

Missing or non-evaluable measurements will not be replaced. The only exception is detailed below.

The number of exacerbations per year will be extrapolated for patients withdrawing from the study to provide an estimate of the number of exacerbations over the one year observation period. The number of exacerbations in a year will be calculated by multiplying the number of exacerbations experienced by the patient by 13 and dividing by the number of 4-week periods the patient was followed up [Stockley R.A., Chopra N, Rice L. Addition of salmeterol to existing treatment in patients with COPD: a 12 month study. *Thorax*. 2006;61:122-128].

$$\text{Number of exacerbations per year} = \frac{\text{Number of exacerbations} * 13}{\text{Number of 4-week observation period intervals}}$$

CONFIDENTIAL

201112 (EPI-NTHI-001 BOD APA)
 Statistical Analysis Plan Amendment 2 Final

The calculation of exacerbation rate will be based on follow-up period intervals of four weeks to avoid obtaining high imputed rates if a patient withdrew very early from the study after experiencing an exacerbation. Four-week intervals will be adopted since treatment courses for moderate/severe exacerbations are <=2 - 4 weeks when appropriate.

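### The SAP leaves an AECOPD with an unknown end date out of episode length but gives it an average length in the percentage-of-days table; if follow-up stopped mid-episode, this shortens the duration summaries

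*SAP*

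**What the plan says.** Protocol 3.1.1.1 ties the end of an AECOPD to a judgement made during follow-up: "The end date should be based on when the investigator determines that the AECOPD symptoms have resolved". If contact stops before that judgement, no end date exists.

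The current SAP (Amendment 2) then uses two treatments.

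- **Episode length.** SAP 6.3.5 plans descriptive statistics on the "average length of AECOPD episodes, as estimated by the investigator, will be presented, for any, mild, moderate and severe AECOPD". SAP 11.3.1 governs missing dates for this output: "Partial or missing initial and end dates for exacerbation will not be considered to measure the length of an exacerbation".
- **Percentage of days.** SAP 6.3.5 also plans "Descriptive statistics of the number of patients according to their percentage of days within an exacerbation period", relative to the total observation period. The rule here is confined to this one output and keeps episodes without a known end date. Each of them receives a substitute value, described only in these words: "the length was estimated by the investigator as the average length per severity grade".

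SAP 11.3 states the general principle: "Missing or non-evaluable measurements will not be replaced. The only exception is detailed below". The exception it goes on to describe is the extrapolation of the yearly exacerbation count for patients who withdraw. Protocol 8.2 says that what was collected before withdrawal or last contact is used in the analysis.

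No section says what to do with an episode still open at last contact or at death. For EXACT-PRO, SAP 12.2 defines recovery as the score returning to baseline and makes no provision for a score that has not done so by last contact.

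**The concern.** An episode cut off by loss of follow-up is not an episode without information: it lasted at least as long as it was observed. The longer an episode runs, the more opportunity there is for contact to be lost during it, so the open episodes are longer on average than those that close. Summarising only the closed ones pulls duration down.

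Filling in an average for the severity grade does not repair this if the average comes from closed episodes. It also cannot be reproduced as written, because SAP 6.3.5 does not say whose average it is or which episodes it is taken from.

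Duration overall and by severity is a secondary endpoint (SAP 4.2), and the use of EXACT-PRO to fix the end date is a tertiary objective (SAP 3.3). Both depend on how open episodes are counted.

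**Working it through.** **1. The passages side by side**

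| Section | Output | Episode with no end date | In conflict with |
|---|---|---|---|
| SAP 11.3.1 | Episode length | Left out | Protocol 8.2, if follow-up stopped mid-episode |
| SAP 6.3.5 | Percentage of days | Kept at an average length | SAP 11.3, which allows one other exception only |

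**2. Inputs.** The documents give no duration, spread or count of open episodes, so there is no stated figure to reproduce. The usable planning inputs are in Protocol 9.2: about 200 enrolled, 80% completing (200 × 0.80 = 160, as the protocol states), and on average 1 AECOPD visit per subject. Everything else below is an assumption.

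**3. Direction, by hand.** Let lengths be exponential with mean μ and let contact be lost at a constant daily hazard λ during an episode. Then the share open is λμ/(1+λμ) and the mean of closed episodes is μ/(1+λμ). Take μ = 14 days and withdrawal unrelated to the episode:

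- λ = −ln(0.80)/365 = 0.000611, so λμ = 0.00856
- share open = 0.00856/1.00856 = 0.85%
- mean of closed episodes = 14/1.00856 = 13.88 days, that is −0.85%

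**4. Imputing equals dropping.** With n_c closed episodes of mean m and n_o open episodes each given m, the mean is (n_c·m + n_o·m)/(n_c + n_o) = m. The imputed total of exacerbation days is low by the same percentage.

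**5. Simulation.** Inputs: 20% withdrawing in a year and 1 AECOPD per subject-year. Assumed: true mean 14 days; exponential lengths or log-normal with coefficient of variation 0.75; withdrawal hazard during an episode equal to HR times that outside it; Visit 3 postponed until stable.

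| HR | Open per 200 patients | Share open | Bias in mean length |
|---|---|---|---|
| 1 | 1.4 | 0.8% | −0.4% to −0.8% |
| 5 | 6.2–6.4 | 3.6–3.7% | −2.0% to −3.6% |
| 20 | 16.3–16.4 | 9.4–9.5% | −5.1% to −9.4% |
| 50 | 24.7–25.1 | 14.1–14.4% | −7.9% to −14.2% |

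Variations, exponential lengths: a true mean of 7 or 28 days gives −0.5% or −1.8% at HR 1, and −5.9% or −13.6% at HR 20. A rate of 0.2 or 3 per year at HR 20 gives −13.6% or −5.9%.

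**6. Censoring at last contact.** In all these scenarios the Kaplan-Meier mean is within 0.4% of the truth. At HR 20 with exponential lengths, the true mean and median are 14.0 and 9.7 days; closed episodes give 12.7 and 8.8; Kaplan-Meier gives 14.0 and 9.7. This holds because loss within an episode does not depend here on its remaining length.

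**7. Percentage-of-days table.** Of the open episodes, 24–39% had already been observed for longer than the closed-episode mean. The other 61–76% would be given days after last contact. For example, with an assumed grade average of 28 days, an episode lost on day 30 forfeits 2 observed days. With an assumed average of 14, an episode lost on day 3 gains 14 − 3 = 11 days that nobody observed.

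**8. When loss depends on length.** For severe episodes with assumed log-normal lengths (log-SD 0.8, true median 20.3 days), and contact lost in 15–22% and more often in long ones, closed episodes give a median of 18.3–17.1 and Kaplan-Meier 19.4–18.8. The recovered share is (19.4 − 18.3)/(20.3 − 18.3) = 55% to (18.8 − 17.1)/(20.3 − 17.1) = 53%.

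**The case against.** A reader might infer that the SAP gives two conflicting instructions for the same table. It does not: the 6.3.5 rule is confined to the percentage-of-days analysis, and 11.3.1 governs length. A reader might also infer that these are rules for withdrawal or death, or that both remove the long episodes. Neither passage names withdrawal or death; they apply because they cover any unknown end date. The 6.3.5 rule removes nothing, and open episodes are longer on average, not all long.

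The study has safeguards. Calls continue at least every two weeks until resolution, medical records are sought when a visit cannot take place (Protocol 3.1.1), three phone attempts follow a missed visit (Protocol 8.2), and Visit 3 may exceptionally fall outside its window (Protocol Table 6). All analyses are descriptive (SAP 7). These points limit the number of open episodes but do not supply a rule for those that remain.

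The strongest objection concerns the remedy. An end date may also be missing because medical records are incomplete for a patient who stays in the study. Censoring such an episode at last contact could turn an ordinary episode into one of months. Suppose 2–5% of episodes are affected and last contact is 180 days after onset. Mean in-episode days then rise from 14 to 0.98 × 14 + 0.02 × 180 = 17.3, or to 0.95 × 14 + 0.05 × 180 = 22.3, an error larger than the one being corrected. Death is not ordinary censoring either, and a fatal episode may be short. Both points stand, and the fix has to be confined accordingly.

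**Conclusion.** The point holds in a limited form. The SAP treats an unknown end date in two ways, and the 6.3.5 imputation contradicts SAP 11.3. For episodes cut off by loss of follow-up, exclusion from length contradicts Protocol 8.2 and biases duration downward. In the percentage-of-days table the assigned length can fall short of what was observed or extend beyond the observation period.

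Size is uncertain. Under the assumptions above, the bias in mean duration is below about 2% when withdrawal is unrelated to the episode, and about 5–14% when the withdrawal hazard is 20 to 50 times higher within episodes. In a run where half of withdrawals fell at episode onset whatever the length, it was only −0.4%. For the percentage-of-days table, the same size applies only if the average comes from closed episodes, which the SAP does not say. A stronger reading, that severe episodes suffer most and the gradient by severity is flattened, is plausible but has no support in the documents, which give no loss rates by severity.

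**What to change.** 1. Only for episodes unresolved when the patient's follow-up stopped, censor duration at last contact (SAP 6.3.5 and 12.1). Add the Kaplan-Meier median and quartiles for any, mild, moderate and severe AECOPD beside the planned mean, SD and quartiles, which Protocol 9.6 already commits to. Report the number of open episodes by severity.
2. In the percentage-of-days table, count the observed days of those episodes up to last contact, and end numerator and denominator on the same date. SAP 6.3.4 ends the observation period of a patient lost to follow-up at the last visit performed, which may precede the last call or diary entry.
3. For patients still followed whose end date is unknown for another reason, do not censor at last contact. Either exclude the episode or keep the average-length value, naming its source and listing it as an exception in SAP 11.3.
4. Give death during an episode its own rule: a competing event, or a stated end of the episode.
5. Apply the same rule to EXACT-PRO duration when the score has not returned to baseline at last contact (SAP 12.2).

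The cost is SAP wording and one additional summary. PROC LIFETEST and censoring at last contact are already in SAP 6.3.5.2.1 for time to first exacerbation, and no new data are needed. The limitation to state in the report is that Kaplan-Meier corrects only in part if loss depends on episode length.

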11.3.2. Missing data for electronic Diary Card alert

- Days with missing data will not be ignored when defining start of an e-diary signal: e.g., if a patient has two qualifying symptoms followed by a missing day, if the next day with data has two qualifying symptoms this will not be defined as an exacerbation. Hence, the start of an e-diary signal of an exacerbation will require 2 consecutive non-missing days of worsening. If there is partially recorded symptom data at a visit, however, only the observed values will be considered but the day will not be discarded.
- Days with missing data will be ignored when defining end of an e-diary signal of an exacerbation: e.g., if a patient has two days missing in the baseline period and one day missing in the 3- day moving average, both baseline and 3-day moving average values will be calculated using observed data only. Similar rules will apply when there is partially recorded symptom data at a visit (and daily average values will be calculated among the observed values).
- All available data will be used for each patient.
- As a general rule, the baseline symptom count score, and 3 day moving averages are calculated as the average count score of the observed days in the baseline period. For example, if an e-diary signal occurs from day 10 onwards, the baseline period will be the average between day1 and day2 (day1 being the first study day). If day 13 is missing, the 3 day moving average at day 14 will only take into account day 14 and day 15.
- If there are more than 2 consecutive days of missing data after an e-diary signal not resolved, the e-diary signal will not be considered resolved until the next day with observed data if the corresponding moving average is below the baseline value. In other words, if the 3-day average daily score is missing, the day will be counted in the duration of the episode.

CONFIDENTIAL

201112 (EPI-NTHI-001 BOD APA)
 Statistical Analysis Plan Amendment 2 Final

11.4. Number of decimals

The following decimal description will be used for the analyses.

Parameters	Number of decimal digits
% of count, including LL & UL of CI	1
p-value	3
Mean, median	Number of decimals in the raw data + 1
SD	Number of decimals in the raw data + 1
Minimum, maximum, range	Number of decimals in the raw data

LL = Lower Limit UL = Upper Limit CI = Confidence Interval

SD = Standard deviation

11.5. Methodology for computing CI

- All CI computed will be two-sided at 95% significant level.
- The exact 95% CIs for a proportion within a group will be calculated using Clopper Pearson method [[Clopper 1934](#)].

12. ANNEX 2: AECOPD DEFINITION AND CALCULATION RULE**12.1. Definition, onset, recovery, duration of an AECOPD event**

AECOPD events are confirmed according to investigator judgment after an AECOPD visit which is aimed to exclude worsening in symptoms not related to an AECOPD event.

AECOPD visits are scheduled after an electronic Diary Card alert confirmed by the investigator (by phone call or at the study site) or after spontaneous site visits due to worsening symptoms without any alert.

Electronic Diary Card alerts refer to daily symptoms recorded the morning after (also called morning symptoms). Alerts are based on the Anthonisen criteria:

- Worsening of two or more of the following major symptoms for at least two consecutive days*^{***}: dyspnea, sputum volume, sputum purulence (colour)

Or

- Worsening of any major symptom together with any of the following minor symptoms for at least two consecutive days*^{***}: sore throat, colds (nasal discharge and/or nasal congestion), fever (oral temperature $\geq 37.5^{\circ}\text{C}$) without other cause, increased cough, increased wheeze.

** The same two symptoms do not have to be present on both days as long as at least one major symptom is present on both days.*

CONFIDENTIAL

201112 (EPI-NTHI-001 BOD APA)
 Statistical Analysis Plan Amendment 2 Final

AECOPD onset will be defined as the first day of the two consecutive days of worsening symptoms.

AECOPD recovery will be determined/confirmed by the investigator/delegate during (a) follow-up phone call(s) which will take place every 2 weeks until the AECOPD has resolved. The end date will be based on when the investigator/delegate determines that the AECOPD symptoms have resolved. In determining this end date, consideration will be given to symptoms recorded in the electronic Diary Card and patient assessment during the phone calls.

AECOPD duration will be defined as the number of days from AECOPD onset (included) and AECOPD recovery (not included).

Duration = date2 – date1 + 1,

with date2: AECOPD recovery date,

date1: AECOPD onset date

12.2. Recovery and duration of an exacerbation according to EXACT-PRO:

An EXACT-PRO AECOPD event is defined as a 12 point increase above baseline for 2 consecutive days, or a nine point increase for 3 consecutive days.

The baseline EXACT-PRO score is calculated as the average daily EXACT-PRO score over days 14 to 8 preceding AECOPD symptomatic onset.

AECOPD recovery according to EXACT-PRO corresponds to the day at which the EXACT-PRO score return to its baseline value (or below) [Mackay AJ, Donaldson GC, Patel AR, Singh R, Kowlessar B, Wedzicha JA. Detection and severity grading of COPD exacerbations using the exacerbations of chronic pulmonary disease tool (EXACT). *Eur Respir J*. 2014;43(3):735-44.].

The AECOPD duration according to EXACT-PRO will be defined as the number of days from AECOPD onset (included) and AECOPD recovery according to EXACT-PRO (not included).

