9.7. Analysis of tertiary objectives

Descriptive statistics (median, mean, range, standard deviation, first and third quartiles) on the end date of AECOPD as provided by the investigator or estimated by EXACT-PRO (via a specific algorithm which will be detailed in the Statistical Analysis Plan) will be presented.

Descriptive summaries of the quantity of specific bacteria at each scheduled [stable] and exacerbation visit will be provided for both culture and PCR analysis.

Descriptive summaries of the quantity of specific viruses at each scheduled [stable] and exacerbation visit will be provided for PCR analysis.

A conditional logistic model will be fitted to estimate the odds ratio of being in a stable state vs. an exacerbation state given the presence or not of several bacterial pathogens found by bacteriological culture and by country. The same model will also be performed for bacterial and viral pathogens found by PCR.

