4.2. Secondary endpoints

- Occurrence of potential bacterial pathogens in sputum of stable COPD patients and during AECOPD, as measured by real-time qualitative PCR/ quantitative PCR and compared to data from bacteriological methods, over the course of 1 year:
 - Including (but not necessarily limited to) *H. influenzae*, *M. catarrhalis*, *S. pneumoniae*, *S. aureus* and *P. aeruginosa*.
- Occurrence of potential bacterial and viral pathogens (overall and by species) in sputum of stable COPD patients by GOLD grade, over the course of 1 year.
- Occurrence of potential bacterial and viral pathogens (overall and by species) in sputum during AECOPD by severity of AECOPD, over the course of 1 year.
- Incidence rate (per patient per year) of AECOPD, overall and by GOLD grade, over the course of 1 year.
- Severity of AECOPD, overall and by GOLD grade, over the course of 1 year.
- Duration of AECOPD, overall and by AECOPD severity, over the course of 1 year.
- CAT score in stable COPD patients and during AECOPD, over the course of 1 year.
- SGRQ-C score in stable COPD patients, over the course of 1 year.
- FEV₁% of predicted normal value in stable COPD patients, at Pre-Month 0 and Month 12.
- Healthcare utilisation, over the course of 1 year.

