6.4.1. End date of AECOPD using EXACT-PRO

Descriptive statistics (N, mean, median, standard deviation, minimum and maximum, first and third quartiles) on the average length of AECOPD episodes, as estimated through the EXACT-PRO (section 12), will be presented, for any, mild, moderate and severe AECOPD.

The frequency distribution of exacerbation confirmed at site visit or through medical records (with or without morning symptoms diary alert) will be tabulated versus EXACT-PRO exacerbations.

Descriptive statistics (N, mean, median, SD, minimum, maximum, first and third quartiles) for the EXACT daily scores will be tabulated at baseline, during the day before exacerbation, at exacerbation onset and at recovery according to investigator judgement. These statistics will be reported overall and for any mild, moderate or severe exacerbation visit.

Graphs detailing the EXACT-PRO scores before, during and after exacerbation onset as defined clinically will be also presented.

Difference from baseline, with 95% CI, of EXACT score measured at stable scheduled visit will be plotted.

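### SAP 12.1 gives two incompatible rules for AECOPD duration: the sentence means date2 − date1, but the formula under it adds one day

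*SAP*

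**What the plan says.** SAP 12.1 defines investigator-based duration twice, on adjacent lines. In words: "AECOPD duration will be defined as the number of days from AECOPD onset (included) and AECOPD recovery (not included"). As a formula: "Duration = date2 – date1 + 1", where date1 is the onset date and date2 the recovery date. The same section sets onset at the first of the two consecutive days of worsening, and bases the end date on when the investigator or delegate judges that symptoms have resolved. SAP version 1 and SAP Amendment 1 carry the same sentence and formula, so the pair has stood through both amendments.

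SAP 12.2 defines the EXACT-PRO duration with onset included and "recovery according to EXACT-PRO (not included"), and gives no formula.

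The quantity is used as follows:

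- SAP 4.2 lists it as a secondary endpoint: "Duration of AECOPD, overall and by AECOPD severity, over the course of 1 year".
- SAP 6.3.5 plans descriptive statistics on the "average length of AECOPD episodes, as estimated by the investigator, will be presented, for any, mild, moderate and severe AECOPD".
- SAP 6.3.5 also plans a summary of the "percentage of days within an exacerbation period out of the total observation period as estimated by the investigator", without stating how days are counted.
- SAP 6.4.1 plans the same set of statistics "on the average length of AECOPD episodes, as estimated through the EXACT-PRO".

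**The concern.** A sentence that excludes the recovery day and a formula that includes it cannot both be the definition. Two programmers working from the same SAP, one from the sentence and one from the formula, would produce different tables for a secondary endpoint, and neither would have departed from the plan.

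The second issue is comparability. The EXACT-PRO duration has only the exclusive wording. If 12.1 is programmed from its formula and 12.2 from its words, an episode with the same recovery date under both methods shows a one-day difference in length. SAP 6.3.5 and 6.4.1 report the two lengths with the same statistics and the same severity breakdown. A reader who compares them could take that day for a real difference between investigator and EXACT-PRO, when it comes only from the day count.

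**Working it through.** **Inputs.** The sentence, the formula and the labels of date1 and date2 are from SAP 12.1. The EXACT-PRO wording is from SAP 12.2. Visit intervals are from Protocol Table 6: optimal 182 days, allowed 175 to 203 days, for each of the two six-month intervals. Neither document gives an expected AECOPD duration, so 7, 10 and 14 days are assumed for illustration.

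**Step 1: count the days.** Take onset on day 1 and recovery on day 8.

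- Sentence: days 1 to 7 are counted, so 8 − 1 = 7 days.
- Formula: 8 − 1 + 1 = 8 days, which is days 1 to 8 with the recovery day counted.

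Listing the calendar days for every gap from 0 to 60 days gives the same result throughout. Onset in and recovery out always gives date2 − date1. Only counting both end days gives the printed date2 − date1 + 1.

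**Step 2: look for a reconciling reading.** The two lines would agree if date2 were the last symptomatic day, that is, the day before recovery. The SAP labels date2 as the recovery date, which is the day that the sentence excludes. That reading is therefore not available.

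**Step 3: effect on the duration tables.** Write d for the worded duration. The formula gives d + 1 for every episode.

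| Statistic | Effect of using the formula |
|---|---|
| Mean, median, quartiles, minimum, maximum | +1 day |
| SD | 0 |
| Difference between severity grades | 0 |

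Relative size at the assumed durations:

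| Worded duration (days) | Formula (days) | Excess |
|---|---|---|
| 7 | 8 | 1/7 = 14.3% |
| 10 | 11 | 1/10 = 10.0% |
| 14 | 15 | 1/14 = 7.1% |

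**Step 4: percentage of days in exacerbation, only if 6.3.5 uses the same formula.** The SAP does not say that it does.

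- Planned Visit 1 to Visit 3 span: 2 × 182 = 364 days. One event adds 1/364 = 0.27 percentage points; three events add 3/364 = 0.82 points.
- Allowed span: 2 × 175 = 350 to 2 × 203 = 406 days. One event adds 1/350 = 0.29 to 1/406 = 0.25 points.
- This range applies only to patients who complete within the windows. If a patient's observation ended at a Visit 2 held on day 175, one event would add 1/175 = 0.57 points.

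**Step 5: what does not use the formula.** Protocol 9.7 describes statistics "on the end date of AECOPD as provided by the investigator or estimated by EXACT-PRO"; these concern dates, not lengths. The incidence rates count events over follow-up time, and the primary endpoint is a proportion of positive sputum. None of these changes.

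**The case against.** The strongest objection is that the documents do not prove which line was intended. The formula is as much a part of the SAP as the sentence. SAP 12.1 uses end date and recovery interchangeably, and the eCRF item is an end date. If sites entered the last symptomatic day there, adding one would be the right count of symptomatic days, and the error would lie in the sentence and in the label of date2.

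This has limited support in the text. Both Protocol 3.1.1.1 and SAP 12.1 tie the end date to the resolution of symptoms; neither ties it to the last day with symptoms. The exclusive wording appears in 12.1 and again in 12.2, whereas the added day appears only in the 12.1 formula. Nor is the added day needed to avoid zero-length episodes, because onset is the first of at least two consecutive days of worsening.

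The other objections concern weight, and they stand as limits:

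- All analyses are descriptive (SAP section 7), and the sample size in Protocol 9.2 does not use duration.
- The shift is constant and can be reversed.
- The mismatch with EXACT-PRO arises only if 12.1 follows its formula and 12.2 its words, and SAP 6.4.1 plans no statistic for the difference between the two lengths.
- The effect on the percentage of days is conditional, because the SAP does not link that analysis to the formula.

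None of these removes the contradiction.

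**Conclusion.** The concern holds. SAP 12.1 contains two definitions of a secondary endpoint that differ by one day for every episode, and no passage in either document says which governs. This is an error as written, not a missing detail.

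The one-day size is exact and needs no assumption. The 7% to 14% figures rest on assumed durations of 7 to 14 days, and the percentage-of-days figures on the unstated premise that 6.3.5 uses the printed formula. The worded definition, date2 − date1, is the better supported of the two. The point should be fixed before the duration tables are finalised, but it affects no inference, no contrast between severity grades and no primary result.

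**What to change.** - In SAP 12.1, replace the formula with Duration = date2 − date1, keeping date2 as the recovery date, so that it agrees with the sentence.
- In SAP 12.2, print the same formula with the EXACT-PRO recovery date as date2.
- In SAP 6.3.5 and 6.3.8, state that days in exacerbation are counted by this rule, so that the percentage of days and the healthcare use per day follow the same count.
- Check that the derived-data program follows the corrected rule.

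If the sponsor does intend to count the recovery day, the wording in both 12.1 and 12.2 has to change instead; the two lines in 12.1 cannot both stay.

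The cost is one line in each of 12.1 and 12.2, two cross-references and a program check. No new data and no new analysis are needed.
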